5.4.4.1. Analysis of immune responses to disease as planned in the protocol

- *For example, for levels of neutralizing antibodies to RSV-B:*
 - GMTs/ GMCs may be tabulated with 95% CI.
 - Percentage of subjects above various thresholds, depending on the antibody tested, may be tabulated with exact 95% CI.

5.4.4.2. Additional Considerations:

N/A

5.5. COVID-19 Supplement

5.5.1. In addition to satisfying local reporting requirements for COVID-19 cases, maternal and infant COVID-19 cases identified within the existing framework of the study will be captured and reported on the COVID-19 eCRF for the study.

COVID-19 cases should be reported in the eCRF according to the WHO Case Definition [[WHO, 2020](#)]. Please refer to Section 11 using one of the following terms:

- Suspected COVID-19 infection
- Probably COVID-19 infection
- Confirmed COVID-19 infection

5.5.2. Additional Considerations

5.5.2.1. WHO Case Definition (March 20, 2020 Version):

Suspected case

- a. A patient with acute respiratory illness (fever and at least one sign/symptom of respiratory disease, e.g., cough, shortness of breath), AND a history of travel to or residence in a location reporting community transmission of COVID-19 disease during the 14 days prior to symptom onset;

OR

- b. A patient with any acute respiratory illness AND having been in contact (see definition of “contact” below) with a confirmed or probable COVID-19 case (see definition of contact) in the last 14 days prior to symptom onset;

OR

- c. A patient with severe acute respiratory illness (fever and at least one sign/symptom of respiratory disease, e.g., cough, shortness of breath; AND requiring hospitalization) AND in the absence of an alternative diagnosis that fully explains the clinical presentation.

Probable case

- a. A suspect case for whom testing for the COVID-19 virus is inconclusive (Inconclusive being the result of the test reported by the laboratory).

OR

- b. A suspect case for whom testing could not be performed for any reason.

Confirmed case

A person with laboratory confirmation of COVID-19 infection, *irrespective of clinical signs and symptoms*.

A contact is a person who experienced any one of the following exposures during the 2 days before and the 14 days after the onset of symptoms of a probable or confirmed case:

- 1. Face-to-face contact with a probable or confirmed case within 1 meter and for more than 15 minutes;
 - 2. Direct physical contact with a probable or confirmed case;
 - 3. Direct care for a patient with probable or confirmed COVID-19 disease without using proper personal protective equipment;
- OR
- 4. Other situations as indicated by local risk assessments.

Note: for confirmed asymptomatic cases, *the period of contact* is measured as the 2 days before through the 14 days after the date on which the sample was taken which led to confirmation.

5.5.2.2. Reporting COVID-19 cases—Maternal and Infant Subjects

Frequency of COVID-19 cases (suspected, probable, and confirmed) will be reported for mothers and infants.

Frequency of mothers and infants who had a COVID-19 diagnosis and test performed and number of subjects with positive, negative, and indeterminate results will be reported.

Incidence of COVID-19 confirmed cases will be reported for mothers.

6. ANALYSIS INTERPRETATION

Analyses will be descriptive with the aim to characterize different sub-groups of women. These sub-groups will be defined prior to analyses and will be related to e.g. risk factors for maternal and neonatal events of interest and endemic disease. These descriptive analyses should be interpreted with caution considering that there is no adjustment for multiplicity for these comparisons.

7. CONDUCT OF ANALYSES

All analyses will be done on cleaned data.

Analyses will be performed in a stepwise manner after all subjects in all countries have completed all study visits in Epoch 002 and again after completion of all study visits in Epoch 003.

Analyses of pregnancy outcomes, pregnancy related events of interest, and neonatal events of interest will be performed when all data up to 42 days post-delivery are available (Epoch 002). For these analyses a statistical report but no CSR will be prepared.

Final analyses will be performed when all data up to study end are available (Epoch 002 and Epoch 003). An integrated CSR including all available data will be written and made available to the investigator(s).

If the data for tertiary endpoints become available at a later stage, additional analysis/analyses will be performed. These data will be documented in annex(es) to the study report and made available to the investigators.

Additional analyses may be performed if deemed necessary to inform the design or implementation of future clinical trials.

Any deviation(s) or change(s) from the original statistical plan outlined in this protocol will be described and justified in the final study report.

Interim analysis for RSV LRTIs

If deemed necessary, an interim analysis **may** be performed on RSV surveillance data as part of the secondary objective of determining incidence of RSV LRTI. This interim analysis **may** be performed to obtain preliminary information on the performance of the case definitions used for RSV LRTI, severe LRTI, and very severe LRTI ([Table 3](#)) and to assess levels of RSV neutralising antibody in maternal and cord blood at delivery. The interim analysis **may** occur after the database freeze at the time point when approximately 50% of infants will have completed up to 6 months of follow up during the surveillance period following birth (up to Visit 3-NB). **If an interim analysis is performed**, data cleaning plans will be scheduled as needed to supply data for interim analyses in a timely manner. This interim analysis **may** be performed on data that is as clean as possible. Preliminary results will be made available in a timely manner for use in the potential adjustment of the RSV LRTI case definitions to be used in pivotal clinical trials scheduled to begin shortly thereafter. The results pertaining to this analysis (**if performed**) will be purely descriptive, with no adjustment of type I error, and will be reported in an interim statistical report. No CSR will be prepared.

7.1. Sequence of analyses

Description	Analysis ID	Disclosure Purpose (CTRS=public posting, SR=study report, internal)	Dry run review needed (Y/N)	Study Headline Summary (SHS)requiring expedited communication to upper management (Yes/No)
Month 12	E1_01	CTRS Study report	Yes	Yes
Month 6 interim analysis- may occur	E1_02	Internal	Yes	No
Analysis of epoch 2	E1_03	Internal	Yes	No

Analysis ID will depend on whether interim and epoch 2 analysis will be run using the same DBF depending on availability of lab results.

8. CHANGES FROM PLANNED ANALYSES

Only the first episode within a given age interval is considered for the computation of incidence. The incidence of event is computed using three different calculation methods: incidence rate, proportion affected, and incidence proportion. See section 5.3.6 for details of calculation.

In analysing incidence of RSV LRTI and RSV Hospitalization, only the first episode of each will be considered.

A correction from the analysis planned in protocol in section 5.3.5.1 is that we will be reporting on all cause LRTIs and RSV associated LRTIs.

Analyses will be stratified by country and by age strata (mother or infant depending on the analysis).

In instances where there are low frequencies (either in events of interest or case definitions) results may be presented by region in addition to by country (see Section 9.3 for subgroups).

The cohort have been adjusted in Amendment 4 of the protocol. See section 4 in the SAP for details. Analyses will be conducted on PPS cohorts. If there is a difference of 5% or more between the number of participants in the enrolled set and the PPS, analyses will also be performed on enrolled sets.

India has been removed from the study and Bangladesh and Panama have been added.

Alternative LRTI/Severe LRTI case definitions have been added to the study and subsequent analyses.

The interim analyses is no longer planned and may only occurred if deemed necessary.

Considering the COVID19 pandemic, Primary analysis (all subjects have completed all study visit in Epoch 002) will be conducted using as clean as possible data based on the status of the data monitoring defined by the pre-defined proportion of Maternal Subjects Assigned to the SDV/SDR Scheme defined in the monitoring plan.

In addition to the pre-defined analysis, sensitivity analysis will be also conducted, as appropriate, based on the % of maternal and infant subjects reaching the threshold of 70% SDV/SDR scheme as defined in the monitoring plan.”

9. NON-STANDARD DATA DERIVATION RULES AND STATISTICAL METHODS

9.1. Data Derivation

9.1.1. Maternal blood and cord blood

Antibody titres will be obtained from maternal blood and cord blood at delivery. The GMT/GMC and its 95% CI will be obtained by exponentiating the mean and its 95% CI of the log-transformed titres/concentrations. All CI computed will be two-sided 95% CI.

9.1.1.1. Assay cut-offs for serology results

A seronegative subject is a subject whose antibody titre is below the cut-off value of the assay. A seropositive subject is a subject whose antibody titre is greater than or equal to the cut-off value of the assay. The cut-off tests for immunogenicity evaluation will be as per following:

Table 7 Derivation rule for GMT calculation and seropositivity status with respect to RSV A and RSV B neutralizing antibody titers in maternal blood at delivery and cord blood

System	Component	Method	Unit	Cut-off *(LLOQ)	ULOQ
Serum	RSV-A Neutralising Antibody	NEU	ED60 and/or IU (international unit)	18 for ED60 56 for IU	ED60 : 123535 IU : 217400
Serum	RSV-B Neutralising Antibody	NEU	ED60 and/or IU (international unit)	30 for ED60 7 for IU	N/A

RSV = respiratory syncytial virus; ED60 = serum dilution inducing 60% inhibition in plaque forming units; IU/ml = International units/milliliter, IU= International units

Assay cut-off and unit might be subject to change before starting of testing (e.g. in case of requalification, revalidation or standardisation). In this case, this will be documented in the clinical report.

Assay	Raw result	Derivation for GMT calculation	Derivation of positivity status
RSV-A and RSV-B neutralizing antibody	<LOD	LOD/2	Negative
	≥LOD	Exact value	Positive

LOD=18 ED₆₀

9.1.2. Nasal swabs from infants during RSV LRTI episodes

The sponsor will analyze nasal swabs by quantitative reverse transcription polymerase chain reaction (RT-PCR) for the presence of RSV A/B. A positive (RSV A or B) test result constitutes a case of RSV infection, if viral load is greater than or equal to the cut-off value of the assay

Table 8 RSV positivity status in infants will be determined from viral loads from nasal swabs taken during infant visits. The infant will be considered RSV positive according to the following thresholds of copies/mL of RSV antibodies

Component	Method	Unit	Cut-off*
RSV A	RT-qPCR	Copies of RSV A RNA per mL	304 copies/ml
RSV B	RT-qPCR	Copies of RSV B RNA per mL	475 copies/ml

*Assay cut-off and unit might be subject to change before starting of testing (e.g. in case of requalification, revalidation or standardisation). In this case, this will be documented in the clinical report.

Assay	Raw result*	Derivation for GMT calculation	Derivation of positivity status
RSV-A and RSV-B	<LOD	LOD/2	Negative
	≥LOD	Exact value	Positive

*RSV-A : LOD=304 copies/ml

*RSV-B : LOD=475 copies/ml

9.1.3. Risk factors for pregnancy-related and neonatal events of interest

Table 9 Risk factors for pregnancy-related events of interest

Risk Factor	Categories
Prenatal smoking exposure during this pregnancy	Yes/No
Alcohol consumption during this pregnancy	Yes/No
BMI pre-pregnancy (kg/cm ²)	Continuous
Age of mother at delivery in current pregnancy(years)	18-34 ≥35
Subject currently lives in a country or region with Zika transmission	Yes/No
Subject has travelled to a country or region with Zika transmission since the beginning of their pregnancy	Yes/No
Subject travelled to country or region with Zika virus transmission	Yes/No
Predominant geographic ancestry	African Heritage/African American American Indian or Alaskan Native Asian-Central/South Asian Heritage Asian-East Asian Heritage Asian-Japanese Heritage Asian-South East Asian Heritage Native Hawaiian or Other Pacific Islander White Middle-eastern /North African Heritage White-Caucasian/ European Heritage Latino/Mestizo Other
Caesarean section in previous pregnancy	Yes/No
Highest education level of mother	High education Yes: Bachelor's degree or higher No: Less than bachelor's degree

Table 10 Risk factors for neonatal events of interest

Risk Factor	Categories
Prenatal smoking exposure during this pregnancy	Yes/No
Age of mother at delivery in current pregnancy (years)	18-34 ≥35
Alcohol consumption during this pregnancy	Yes/No
BMI pre-pregnancy (kg/cm ²)	Continuous
Gestational diabetes mellitus in current pregnancy	Yes/No
Gestational hypertension in current pregnancy	Yes/No
Fetal growth restriction	Y/N
Antenatal bleeding	Y/N
Dysfunctional labor	Y/N
Gender of new-born	Male/Female
Subject lives in or travelled to country or region with Zika virus infection during pregnancy	Yes/No
Predominant geographic ancestry	African Heritage/African American American Indian or Alaskan Native Asian-Central/South Asian Heritage Asian-East Asian Heritage Asian-Japanese Heritage Asian-South East Asian Heritage Native Hawaiian or Other Pacific Islander White Middle-eastern /North African Heritage White-Caucasian/ European Heritage Latino/Mestizo Other
Apgar at 5 minutes of age	0-3 inclusive 4-6 inclusive 7 or greater

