2. STUDY DESIGN

2.1. Summary

This is a prospective multi-country cohort study that aims to provide information for subsequent clinical trials for maternal immunization for respiratory syncytial virus (RSV). The study will provide background rates of maternal and neonatal events of interest, incidence rates of lower respiratory tract illnesses associated with RSV (RSV LRTI), and will determine the capacity of future sites for clinical trials. Approximately 2300 pregnant women from nine different countries will be enrolled during their third trimester of pregnancy and followed until 42 days after delivery. Their children will be followed from birth until one year of age. Epoch 1 of the study consists of the screening of maternal subjects. Epoch 2 includes visits 1-6 of the mother and visits 1-2 of the new born; during which time data on pregnancy outcomes and maternal and neonatal events of interest will be collected and RSV LRTI surveillance will begin (from visit 1 of the new born). Neonatal events of interest will only include events that occurred during the first 28 days of life, but data on these events can be collected up to one year of age. Maternal and cord blood samples will also be collected from the mother at delivery. Lastly, Epoch 3 will include RSV LRTI surveillance as well as continued recording of neonatal events of interest. During surveillance in Epoch 3, symptoms relevant to RSV illness will be recorded in diary cards, and RSV positivity will be confirmed via laboratory tests performed on nasal swabs collected during site visits.

Please note that when referring to epochs in the SAP, we are following the convention outlined in the protocol. Epochs in the CDISC T domains are named differently and are as follows: For maternal subjects: screening epoch and study procedures epoch. For infants: screening epoch and surveillance epoch (infants do not actually have a screening visit in this study but this is the naming standard used for CDISC T domains).

Figure 1 Study design

D = day; M = month; V = visit; W = week; Y = year. NB = newborn; GA = Gestational age; BS = blood sample; US = urine sample for dipstick testing; IMM = immune response; HB = hematology/biochemistry; RBC = red blood cell(s); WBC = white blood cell(s); RSV = respiratory syncytial virus; RTI = respiratory tract illness; LRTI = lower respiratory tract illness;

Refer to [Table 1](#) for additional information about the analyses indicated above.

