- Sampling schedule for **neonates/infants:** Surveillance for RSV LRTI will be conducted in infants through the 12 month study period. During this 1-year post-birth surveillance period, for each RTI with suspicion of difficulty in breathing, or wheezing, or with parental concern, a nasal swab will be collected at a visit to assess potential RSV associated RTIs/LRTIs.
- Primary Completion Date (PCD): 42 days post-delivery/birth (i.e. Visit 6 for maternal subjects and Visit 2-NB for infant subjects) or last visit of Epoch 002.
- End of Study (EoS): Last testing results released of samples collected up to Visit 4-NB (assays related to primary and secondary endpoints).
- Duration of the study: Approximately 4.5 to 6 months for maternal subjects; approximately 1 year for infant subjects.
 - Epoch 001: Screening
 - Epoch 002: Primary starting at Visit 1 and ending 42 days post-delivery/birth (Visit 6 for maternal subjects and Visit 2-NB for infant subjects).*
 - Epoch 003: Follow-up of infants starting 43 days post-delivery/birth and ending at Visit 4-NB (1 year post-birth).

*Any safety and disease surveillance data collected after Visit 2-NB will be collected in Epoch 003.

Table 2 Study groups and epochs foreseen in the study

Study Groups	Number of subjects enrolled	Age (Min/Max)	Epochs		
			Epoch 001	Epoch 002	Epoch 003
Maternal subjects	Up to ~ 2300	18 years - 45 years	x	x	
Infants	Up to ~ 2300	NA		x	x

Approximately 200 to 300 per country. To achieve the enrollment targets noted above, the number of pregnant women SCREENED in each country may exceed the country-specific enrolment goal.

- Surveillance for pregnancy outcomes and pregnancy-related events of interest that occur from Visit 1 up to 42 days after delivery (Visit 6).
- Surveillance for neonatal events of interest that occur from birth up to 28 days of age.
- Surveillance for RSV LRTI and RSV hospitalization in infants, from birth up to 1 year of age. Nasal swabs will be collected during surveillance visits to confirm RSV positivity.

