Repeat incidence analyses described in section 5.3.6 with alternative LRTIs/Severe LRTIs case definitions.

5.4.4. To determine risk factors for pregnancy related and neonatal events of interest.**5.4.4.1. Analysis of risk factors for pregnancy related and neonatal events of interest as described in the protocol.**

- Both pregnancy related events of interest and neonatal events of interest will be described according to variables collected in the mother's clinical examination and obstetric risk factors. Frequency tables will be generated for categorical variables.
- Furthermore, multiple variable analyses (such as multiple logistic regression for binary outcomes and multiple Poisson/negative binomial and/or other appropriate models for count outcomes) will be conducted to adjust for covariates of interest, provided there are sufficient numbers of events of interest.

5.4.4.2. Additional considerations:

This analysis will be performed on the maternal and infant PPSs depending on whether the risk factors are for pregnancy-related events of interest or for neonatal events of interest.

There are currently 14 potential pregnancy related events of interest and 9 potential risk factors. Likewise, there are 12 potential neonatal events of interest and 13 potential risk factors. (These do not include GAIA subcategories).

Univariate modelling will be done to first determine which risk factors are associated with which event of interest.

For each potential risk factor,

- Frequency tables will be generated as appropriate, for categorical variables.
- Mean, median, standard error, minimum, maximum and number of missing values will be provided as appropriate, for continuous data.

For pairwise distributions

- Cross-tabulations (i.e. two-way frequency tables) will be generated as appropriate, for categorical-categorical pairs;
- Mean, median, standard error, minimum, maximum and number of missing values by category will be provided as appropriate, for continuous-categorical pairs;

Covariates with univariate p-value less than 0.1 will be included in the multivariable model. The number of covariates included in the model will depend on the number of events (at least 10 events per covariates).

Multiple logistic regression, multiple Poisson regression/negative binomial modelling will be used when appropriate only on risk factors and events of interest that were associated in the univariate analysis and provided there are sufficient numbers of events of interest.

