9.5.5.3. Multiple Logistic Regression models

Multiple logistic regression models will be used to test the association between events of interest and risk factors. PROC LOGISTIC or PROC GENMOD can be used. What is tested will depend on how many people are observed with these outcome and risk factors and if they are associated in the univariate analysis.

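### Zika residence is largely a place-level exposure, but the tertiary risk-factor models treat about 2300 women as independent, so its confidence intervals are too narrow for the commoner events

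*SAP*

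**What the plan says.** The points below are from SAP Amendment 2.

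- **Exposure.** In section 9.1.3, Table 9 (pregnancy-related events) includes "Subject currently lives in a country or region with Zika transmission", coded Yes/No, and lists travel items separately. Table 10 (neonatal events) has one combined item: "Subject lives in or travelled to country or region with Zika virus infection during pregnancy".
- **Selection.** The risk-factor section 5.4.4.2 states: "Covariates with univariate p-value less than 0.1 will be included in the multivariable model". At least 10 events per covariate are required.
- **Model.** Section 9.5.5.3: "Multiple logistic regression models will be used to test the association between events of interest and risk factors". On software it says "PROC LOGISTIC or PROC GENMOD can be used". Poisson or negative binomial models are the alternative, and section 9.5.5.2 reports estimates with 95% CIs.
- **Size and places.** Section 2.1: "Approximately 2300 pregnant women from nine different countries will be enrolled", with "Approximately 200 to 300 per country". Section 8 adds "India has been removed from the study and Bangladesh and Panama have been added", and section 9.3 lists ten countries.
- **What is absent.** Country and centre are in neither risk-factor table. Sections 5.4.4.2 and 9.5.5–9.5.6 specify no random effect, clustered variance or place-based degrees of freedom.

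**The concern.** Whether a woman lives in a Zika area is mostly a fact about where she lives. Women at one centre, and often in one country, will nearly all share the same value. A standard logistic or Poisson model takes the standard error of that term from the number of women. Its null distribution therefore describes equal event rates in all places, which is stricter than no effect of Zika residence. Countries also differ in obstetric practice, diagnostic habits and case mix. Any such difference that happens to line up with the exposed places will look like a residence effect.

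The consequence is that residence passes the p<0.1 screen too often and is then reported with an odds ratio whose interval is too narrow. The caution in section 6 gives only the lack of multiplicity adjustment as its reason, so it would not alert a reader to this.

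**Working it through.** The SAP states no error rate or power for this test, so there is no figure of its own to reproduce.

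**Inputs from the SAP.** About 2300 women in ten countries gives 2300/10 = 230 per country, inside the stated 200 to 300. Table 11 has 31 rows. One row is unlabelled and Medellin and Bogota each appear twice, so there are 31 − 3 = 28 distinct named places. The table lists RSV seasons; the SAP does not say which places have Zika.

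**Assumptions not in the SAP.** Event frequency 1–10%; between-place SD of the log-odds 0.1–0.5; about half the places exposed; exposure constant within a place; no true Zika effect. An SD of 0.25 puts 95% of countries within odds ratios exp(±1.96 × 0.25) = 0.61 to 1.63 of the average. An SD of 0.5 gives 0.38 to 2.66.

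**Step 1, design effect.** DE = 1 + (m − 1) × ICC, and actual error = 2 × [1 − Φ(1.96/√DE)], with m = 230.

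- ICC 0.001: DE = 1.23, error 7.7%.
- ICC 0.005: DE = 1 + 229 × 0.005 = 2.15, error 18.1%.
- ICC 0.01: DE = 3.29, error 28.0%.

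**Step 2, simulation.** Place log-odds are drawn from a normal distribution, events are binomial, whole places are exposed, and the univariate log odds ratio has a Wald test at nominal 5%.

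| Exposure set by | Event rate | SD 0 | SD 0.1 | SD 0.25 | SD 0.5 |
|---|---|---|---|---|---|
| Country (10 × 230) | 5% | 5% | 6% | 13% | 33% |
| Country (10 × 230) | 10% | 5% | 7% | 19–20% | 44–45% |
| Country (10 × 230) | 1% | 4% | 4–5% | 6% | 12% |
| Centre (31 × 74) | 5% | 5% | 5% | 8% | 17% |
| Centre (31 × 74) | 10% | 5% | 6% | 10% | 23–24% |

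The centre rows use all 31 table rows as places. With 28 places the excess is the same or slightly larger. At the p<0.1 screen, with country-level exposure and a 5% event rate, residence passes in 21% (SD 0.25) and 41–42% (SD 0.5) of studies.

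**Step 3, cause.** With SD 0 and event rates of 3–10% the same test holds about 5%. A t-test on the place-level log-odds gives 4–5% in every scenario. The excess therefore comes from using women, not places, as the unit.

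**Step 4, adjustment for ancestry.** Ancestry is the one listed covariate that follows place. With event rates of 5–10% and SD 0.2–0.5, adjusting for it still leaves 9–45%. If exposure coincides with Latin America the figure falls to 5–17%, or the Zika term cannot be estimated when ancestry matches region exactly.

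**The case against.** - **Section 8 says in general terms that analyses are stratified by country.** If that governed these regressions, the spurious between-country contrast would disappear. Section 5.4.4.2 does not carry it into the models, though, and a residence term constant within country would then have no estimate. The sentence replaces one problem with another.
- **The plan leaves model choice open.** It permits other appropriate models and names a procedure that can fit clustered data. That is true, but nothing commits the analyst to clustering, and uncorrected GEE with about ten clusters is itself unreliable.
- **The exposure is recorded per woman and may vary within a country.** This stands in part. Variation between centres reduces the inflation, as the centre rows show, and travel is individual.
- **Rare events are barely affected.** This stands for event rates near 1% with small or moderate variation. The events-per-covariate rule also limits their models: 1% of 2300 is 23 events, enough for two covariates.
- **This is a tertiary, descriptive objective.** This stands, and it bounds the importance of the point.

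A reader might infer more than the document supports. The SAP sets no 5% decision rule for this test; 5% is implied by the 95% CI, and p<0.1 only admits a covariate. The background rates for later vaccine trials come from the primary frequency analyses, already reported by country, and no Zika coefficient alters them. Nor can one say how many events would show a false association, because no country-specific rates are given.

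**Conclusion.** The concern holds for the Zika residence item in the tertiary risk-factor analyses. Followed as written, the plan gives that item intervals that are too narrow. For events of about 5–10% frequency and an assumed between-place SD of 0.25–0.5, the nominal 5% univariate error becomes roughly 13–44% if exposure is set by country and about 8–23% if set by centre. At an SD of 0.1 it is 5–7%. For events near 1% it stays close to 5% up to moderate variation and reaches about 12% at SD 0.5 with country-level exposure.

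These sizes depend on the assumed between-place variation, the exposed share and constancy of exposure within a place, none of which the SAP gives. They describe the univariate test; the multivariable result also depends on whether ancestry enters. The direction does not depend on these choices: wherever places differ and exposure follows place, the standard error is too small. The individual travel items in Table 9 are much less affected.

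**What to change.** In sections 5.4.4.2 and 9.5.5.2–9.5.5.3 and Tables 9 and 10:

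1. Analyse residence with place as the unit: a country or centre random intercept, or GEE clustered on place with a small-sample correction, taking degrees of freedom from the number of places.
2. Where residence does not vary within country, report country-level event frequencies only, with no p-value or odds ratio.
3. Split the combined Table 10 item into residence (place level) and travel (individual level), as Table 9 already does.
4. State that the residence contrast is ecological and remains confounded by other differences between countries. A random intercept corrects the interval, not the confounding.
5. Say whether the section 8 sentence on stratification by country applies to these regressions.

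The cost is SAP wording, one derived variable and a different model call. The residence item will have wider intervals, and in some cases no estimate.

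### Previous caesarean is coded Yes/No with no rule for first pregnancies and no parity covariate, so its odds ratio can be biased in either direction for events related to parity

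*SAP*

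**What the plan says.** The factor "Caesarean section in previous pregnancy" stands in "Table 9 Risk factors for pregnancy-related events of interest" (SAP 9.1.3) with two categories, Yes and No. There is no not-applicable level and no coding note. The table has ten rows: smoking exposure, alcohol, pre-pregnancy BMI, maternal age, three Zika items, ancestry, previous caesarean and education. None records parity, gravidity or first pregnancy, and I found none of these terms elsewhere in the SAP. The nearest wording is in section 5.4.4.1, where events are to be "described according to variables collected in the mother's clinical examination and obstetric risk factors"; that is general and names no parity variable.

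The modelling rules are in sections 5.4.4.2 and 9.5.5:

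- Entry: "Covariates with univariate p-value less than 0.1 will be included in the multivariable model".
- Size limit: "at least 10 events per covariates".
- Model: "Multiple logistic regression models will be used to test the association between events of interest and risk factors".
- Software: "PROC LOGISTIC or PROC GENMOD can be used".

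The missing-data rules in section 10.1.2 deal with dates, laboratory results and diary symptoms. A separate missing category is stated for the demographic summaries (5.1.1) and allowed for the event tables (5.2.2.1, 5.2.3.1). No rule covers a missing or not-applicable covariate in a model. Nothing limits the cohort of about 2300 women to those with an earlier birth.

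**The concern.** A woman can have had a previous caesarean only if she has given birth before. The Yes group is therefore entirely parous. Who is in the No group depends on how first pregnancies are coded, and the SAP does not say.

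If first-time mothers are coded No, the contrast is between parous women and a mixture of first-time mothers and parous women without a caesarean. Any effect of parity on the event is then read as an effect of caesarean, and no Table 9 covariate can separate the two. If they are left blank, the result applies only to women with an earlier pregnancy, although the objective concerns all enrolled women. The analysis population would also differ between models that contain the factor and models that do not.

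At stake is whether a published odds ratio for previous caesarean means what a reader will take it to mean.

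**Working it through.** The SAP states no figure to reproduce here. The only planned number used is the sample of about 2300 women (section 2.1). All other inputs are assumptions, shown as ranges.

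**First pregnancies coded No**

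Assumed inputs:

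- share of first pregnancies f = 30%, 40% or 50%;
- previous caesarean in 15% of all women;
- event risk 4% in all parous women, so the true previous-caesarean odds ratio is 1;
- event risk r in first pregnancies.

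The No group is 85% of women. Its risk is

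p(No) = [f × r + (1 − f − 0.15) × 0.04] / 0.85

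and the odds ratio obtained is odds(0.04) / odds(p(No)), with odds(0.04) = 0.04/0.96 = 0.04167.

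Example with f = 30%, r = 6%: p(No) = (0.30 × 0.06 + 0.55 × 0.04)/0.85 = 0.0400/0.85 = 0.04706. The odds are 0.04938, and the odds ratio is 0.04167/0.04938 = 0.84.

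| Risk in first pregnancies | f = 30% | f = 40% | f = 50% |
|---|---|---|---|
| 2% | 1.22 | 1.32 | 1.43 |
| 4% (parity unrelated to event) | 1.00 | 1.00 | 1.00 |
| 6% | 0.84 | 0.80 | 0.76 |
| 8% | 0.73 | 0.67 | 0.61 |
| 12% | 0.57 | 0.49 | 0.44 |

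The share of the No group in a first pregnancy is f/0.85: 35%, 47% and 59%.

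A second set of assumptions gives the same pattern: baseline risk 3% or 10%, and previous caesarean in 20-40% of parous women. The odds ratio is 0.62-0.75 when first pregnancy itself has an odds ratio of 2, and 1.21-1.47 when it has 0.5.

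**Would the biased factor pass the p<0.1 screen?**

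With 2300 women, 0.15 × 2300 = 345 have a previous caesarean and 345 × 0.04 = 13.8 of them are expected to have the event. For f = 30%, r = 6%, the other 1955 women have 1955 × 0.04706 = 92 events. The standard error of the log odds ratio is √(1/13.8 + 1/331.2 + 1/92 + 1/1863) = 0.295. Then z = ln(0.844)/0.295 = −0.58 and p is about 0.56. The same calculation at the expected odds ratio elsewhere gives, for f = 30%, 40% and 50%:

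- r = 6%: p = 0.56, 0.45, 0.36;
- r = 8%: p = 0.28, 0.16, 0.09;
- r = 12%: p = 0.051, 0.014, 0.004.

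Four of these nine scenarios fall below 0.1.

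**First pregnancies left blank**

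Both named SAS procedures drop a record with a missing covariate by default. The loss is 2300 × 0.30 = 690 to 2300 × 0.50 = 1150 women from each model containing the factor. For an event with an assumed 3% risk, expected events fall from 2300 × 0.03 = 69 to 1610 × 0.03 = 48 or 1150 × 0.03 = 35. The 10-events rule then allows 4 or 3 covariates instead of 6.

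**The case against.** No is a literally true answer for a woman with no previous pregnancy. A reader might infer that first-time mothers have no valid value and must drop out; the SAP does not support that. The blank-field case depends on an eCRF and protocol that are not shown. It is a possibility, and its size rests on an assumed share of first pregnancies.

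Other strong readings also go too far:

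- *The bias is protective.* It is so only when first pregnancies carry the higher risk. It reverses when they carry the lower risk and vanishes when parity is unrelated to the event.
- *The reference group is mostly first-time mothers.* On these inputs that holds only near 50% first pregnancies.
- *The confounded factor will enter the multivariable model.* It can, but in most of the scenarios above it does not at the expected value.
- *The other adjusted odds ratios are distorted.* Nothing in the SAP or in this check quantifies that.

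On weight, the objective is tertiary. Section 6 calls the analyses descriptive and to be read with caution, section 5.4.4.2 models only where events suffice, and section 9.5.5.2 lets other models be explored. An exploratory covariate list also need not be exhaustive.

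These points limit the consequence. They do not supply a coding rule. Parity may well be collected on the eCRF, but the SAP fixes the modelling categories and the candidate list, and parity is in neither.

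**Conclusion.** The point holds in a limited form. Following Table 9 literally, with first-time mothers coded No, gives a contrast that mixes previous caesarean with parity, and the plan offers no covariate to separate them. For parity-related events the odds ratio is biased even when caesarean has no effect: 0.76-0.84 or 0.61-0.73 when first-pregnancy risk is 6% or 8% against 4% in parous women, and above 1 when it is lower. These sizes rest wholly on assumed parity, caesarean and event rates, so they illustrate the mechanism and do not predict the result. Under a blank field the problem is instead a restricted analysis population.

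The primary frequencies and the RSV incidence analyses are untouched. It is still worth correcting, because the stated coding is inferior to an available one and the change is small.

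**What to change.** In Table 9, replace the Yes/No row by a three-level factor derived from obstetric history:

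1. no previous birth;
2. previous birth(s) without caesarean (reference);
3. previous caesarean.

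First-time mothers then stay in every model, and the previous-caesarean odds ratio is a comparison among parous women. In the illustration it returns to 1.00. The first level also gives the models a parity term.

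The cost is a change of SAP wording, one derived variable and one extra parameter, which means about 10 more events under the plan's 10-events-per-covariate rule. A lesser alternative is a one-line rule restricting this factor to women with an earlier birth. That removes the mixing but leaves first-time mothers out of those models.

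When the table is edited, the count in section 5.4.4.2 should be brought into line. It reads "There are currently 14 potential pregnancy related events of interest and 9 potential risk factors", while Table 9 lists ten factors; this is a separate, minor discrepancy.
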